7.6.3. Grade 4 Laboratory Abnormality or Clinical Event

For a Grade 4 clinical event or clinically significant Grade 4 laboratory abnormality confirmed by repeat testing that is considered related to IMP, IMP should be permanently discontinued and the subject managed according to local practice. The subject should be followed as clinically indicated until the laboratory abnormality returns to baseline or is otherwise explained, whichever occurs first. A clinically significant Grade 4 laboratory abnormality that is not confirmed by repeat testing should be managed according to the algorithm for the new toxicity grade.

Investigational medicinal product may be continued without dose interruption for a clinically non-significant Grade 4 laboratory abnormality (e.g., Grade 4 creatine kinase [CK] after strenuous exercise or triglyceride elevation that is nonfasting or that can be medically managed) or a clinical event considered unrelated to IMP.

Treatment-emergent toxicities will be noted by the investigator and brought to the attention of the Gilead Medical Monitor, who will have a discussion with the investigator and decide the appropriate course of action. Whether considered treatment-related or not, all subjects experiencing AEs must be monitored periodically until symptoms subside, any abnormal laboratory values have resolved or returned to baseline levels or they are considered irreversible, or until there is a satisfactory explanation for the changes observed.

Any questions regarding toxicity management should be directed to the Gilead Medical Monitor.

7.7. Special Situations Reports

7.7.1. Definitions of Special Situations

Special situation reports include all reports of medication error, abuse, misuse, overdose, reports of adverse events associated with product complaints, occupational exposure with an AE, pregnancy reports regardless of an associated AE, and AE in an infant following exposure from breastfeeding.

Medication error is any unintentional error in the prescribing, dispensing, or administration of a medicinal product while in the control of the health care provider, subject, or consumer.

Abuse is defined as persistent or sporadic intentional excessive use of a medicinal product by a subject.

Misuse is defined as any intentional and inappropriate use of a medicinal product that is not in accordance with the protocol instructions or the local prescribing information.

An overdose is defined as an accidental or intentional administration of a quantity of a medicinal product given per administration or cumulatively which is above the maximum recommended dose as per protocol or in the product labelling (as it applies to the daily dose of the subject in question). In cases of a discrepancy in drug accountability, overdose will be established only when it is clear that the subject has taken the excess dose(s). Overdose cannot be established when the subject cannot account for the discrepancy except in cases in which the investigator has reason to suspect that the subject has taken the additional dose(s).

Product complaint is defined as a complaint arising from potential deviations in the manufacture, packaging, or distribution of the medicinal product.

Occupational exposure is defined as exposure to a medicinal product as a result of one's professional or non-professional occupation.

7.7.2. Instructions for Reporting Special Situations

7.7.2.1. Instructions for Reporting Pregnancies

The investigator should report pregnancies in female study subjects that are identified after initiation of study medication and throughout the study, including the post study drug follow-up period, to Gilead PVE using the pregnancy report form within 24 hours of becoming aware of the pregnancy.

Refer to Section 7.3 and the eCRF completion guidelines for full instructions on the mechanism of pregnancy reporting.

The pregnancy itself is not considered an AE, nor is an induced elective abortion to terminate a pregnancy without medical reasons.

Any premature termination of pregnancy (e.g., a spontaneous abortion, an induced therapeutic abortion due to complications or other medical reasons) must be reported within 24 hours as an SAE. The underlying medical reason for this procedure should be recorded as the AE term.

A spontaneous abortion is always considered to be an SAE and will be reported as described in Section 7.3. Furthermore, any SAE occurring as an adverse pregnancy outcome post study must be reported to Gilead PVE.

The subject should receive appropriate monitoring and care until the conclusion of the pregnancy. The outcome should be reported to Gilead PVE using the pregnancy outcome report form. If the end of the pregnancy occurs after the study has been completed, the outcome should be reported directly to Gilead PVE. Gilead PVE contact information is as follows:

Email: **PPD** and Fax: **PPD**

Refer to [Appendix 7](#) for Pregnancy Precautions, Definition for Female of Childbearing Potential, and Contraceptive Requirements.

7.7.2.2. Reporting Other Special Situations

All other special situation reports must be reported on the special situations report form and forwarded to Gilead PVE within 24 hours of the investigator becoming aware of the situation. These reports must consist of situations that involve study IMP and/or Gilead concomitant medications, but do not apply to non-Gilead concomitant medications.

Special situations involving non-Gilead concomitant medications do not need to be reported on the special situations report form; however, for special situations that result in AEs due to a non-Gilead concomitant medication, the AE should be reported on the AE form.

Any inappropriate use of concomitant medications prohibited by this protocol should not be reported as “misuse,” but may be more appropriately documented as a protocol deviation.

Refer to Section 7.3 and the eCRF completion guidelines for full instructions on the mechanism of special situations reporting.

All clinical sequelae in relation to these special situation reports will be reported as AEs or SAEs at the same time using the AE eCRF and/or the SAE report form. Details of the symptoms and signs, clinical management, and outcome will be reported, when available.

8. STATISTICAL CONSIDERATIONS

8.1. Analysis Objectives and Endpoints

8.1.1. Analysis Objectives

The primary objective of the study is to evaluate the short-term antiviral potency of GS-9131 functional monotherapy compared to PTM GS-9131, each administered once daily with the existing failing ARV regimen, as demonstrated by the proportion of subjects achieving HIV-1 RNA $> 0.5 \log_{10}$ decreases from baseline after up to 14 days of therapy in HIV-1 positive, ARV TE adult subjects with nucleos(t)ide resistant virus.

The secondary objectives of this study are:

Part 1

- To evaluate the efficacy of GS-9131 functional monotherapy as determined by the change from baseline in \log_{10} HIV-1 RNA at Day 11 for Sentinel Cohort 1 and Day 15 for Sentinel Cohort 2 and Randomized Cohort.

Part 2

- To evaluate the safety and efficacy of a regimen containing GS-9131 (60 mg) + BIC + DRV + RTV through 24 weeks of treatment in subjects from Sentinel Cohort 1 who switched from a failing regimen as determined by achievement of HIV-1 RNA < 50 copies/mL at Week 24.
- To evaluate the safety and efficacy of a regimen containing GS-9131 (up to 180 mg) + BIC + TAF through 24 weeks of treatment in Subjects from Sentinel Cohort 2 and Randomized Cohort who switched from a failing regimen as determined by achievement of HIV-1 RNA < 50 copies/mL at Week 24.
- To characterize the PK of GS-9131 following multiple doses of GS-9131 in TE patients.
- To evaluate the number of subjects with treatment-emergent NRTI, PI, and INSTI mutations at the time of virologic failure.

8.1.2. Primary Endpoint

The primary endpoint is the proportion of subjects with plasma HIV-1 RNA decreases from baseline exceeding $0.5 \log_{10}$ at Day 15 in the Randomized Cohort in Part 1.

8.1.3. Secondary Endpoints

The secondary endpoints include:

- The change from baseline in plasma \log_{10} HIV-1 RNA (copies/mL) at Day 11 for Sentinel Cohort 1 and Day 15 for Sentinel Cohort 2 and Randomized Cohort in Part 1.
- Number of subjects with treatment-emergent NRTI, PR, and INSTI mutations at the time of virologic failure.

8.1.4. Other Endpoints of Interest

- The proportion of subjects with plasma HIV-1 RNA < 50 copies/mL as defined by the US FDA Snapshot algorithm at Week 24 in Part 2.
- The change from Part 2 baseline in plasma log₁₀ HIV-1 RNA (copies/mL) at Week 24 in Part 2.
- The change from Part 2 baseline in CD4 cell count (cells/μL) at Week 24 in Part 2.

8.2. Analysis Conventions

8.2.1. Analysis Sets

8.2.1.1. All Enrolled Analysis Set

The all enrolled analysis set includes all subjects who enroll into the study either in the sentinel cohorts or randomized cohort. This is the primary analysis set for by-subject listings.

8.2.1.2. Efficacy

The primary analysis set for efficacy analysis is defined as follows:

8.2.1.2.1. Full Analysis Set (FAS)

Two full analysis sets will be defined, one for the Randomized Cohort in Part 1 and one for Part 2. The FAS for the Randomized Cohort in Part 1 will include all subjects who (1) are randomized to Part 1 Randomized Cohort, and (2) have received at least one dose of study medication in Part 1. Subjects in the Randomized Cohort in Part 1 will be grouped according to the treatment to which they were randomized. The FAS for Part 2 will include all subjects who (1) are enrolled into Part 2, and (2) have received at least one dose of study medication in Part 2.

8.2.1.2.2. Per-Protocol (PP) Analysis Set

The Per-Protocol analysis set will only be defined for the Randomized Cohort in Part 1. The Per-Protocol analysis set will include all subjects who (1) are randomized to Part 1 Randomized Cohort, (2) have received at least one dose of study medication in Part 1, and (3) have not committed any major protocol violation in the randomized cohort in Part 1, including the violation of key entry criteria. Subjects in the PP analysis set will be grouped according to the treatment they actually received.

8.2.1.3. Safety

Two safety analysis sets will be defined, one for the Randomized Cohort in Part 1 and one for Part 2. The safety analysis set for the Randomized Cohort in Part 1 will include all subjects who (1) are randomized to Part 1 Randomized Cohort, and (2) received at least one dose of study drug in Part 1. Subjects in the safety analysis set in Part 1 will be grouped according to the treatment they actually received. The safety analysis set for Part 2 will include all subjects enrolled into Part 2 who have received at least one dose of study drug in Part 2. All the data collected up to 30 days after subjects permanently discontinue their study regimen will be included in the safety summaries.

8.2.1.4. Pharmacokinetics

8.2.1.4.1. Pharmacokinetic Analysis Set for Part 1

8.2.1.4.2. The PK analysis set will include all subjects who (1) are enrolled or randomized into the study, (2) have received at least one dose of study medication and (3) have at least 1 non-missing PK concentration data for any analyte of interest. The PK analysis set will be used for analyses of general pharmacokinetics. Pharmacokinetic Analysis Set for Part 2

8.2.1.4.3. The PK analysis set will include all subjects who (1) are enrolled or randomized into the study, (2) have received at least one dose of study medication and (3) have at least 1 non-missing PK concentration data for any analyte of interest. The PK analysis set will be used for analyses of general pharmacokinetics. PBMC PK Analysis Set

The PBMC PK analysis set will include all subjects who (1) are enrolled or randomized into the study, (2) have received at least one dose of study medication and (3) have at least 1 non-missing PBMC PK concentration data for any analyte of interest. The PBMC analysis set will be used for analyses of general pharmacokinetics.

8.2.1.5. Sentinel Cohort Analysis Set

The Sentinel Cohort analysis set will include all subjects who are enrolled into the Sentinel Cohorts and received at least 1 dose of study medication. Both safety and efficacy data will be analyzed using this analysis set for subjects enrolled in Part 1 Sentinel Cohorts.

8.3. Data Handling Conventions

HIV-1 RNA results of “No HIV-1 RNA detected” and “< 20 cp/mL HIV-1 RNA Detected” will be imputed as 19 copies/mL for analysis purposes.

Natural logarithmic transformation of plasma concentrations and PK parameters will be applied for PK analysis.

Laboratory data that are continuous in nature but are less than the lower limit of quantitation or above the upper limit of quantitation will be imputed to the value of the lower or upper limit plus or minus one significant digit, respectively (e.g., if the result of a continuous laboratory test is < 20, a value of 19 will be assigned).

Missing data can have an impact upon the interpretation of the trial data. In general, values for missing data will not be imputed. However, a missing pre-treatment laboratory result would be treated as normal (i.e., no toxicity grade) for the laboratory abnormality summary.

All available data for subjects that do not complete the study will be included in data listings.

8.4. Demographic Data and Baseline Characteristics

Demographic and baseline characteristics will be summarized for each part and cohort (Part 1) using standard descriptive methods including sample size, mean, SD, median, Q1, Q3, minimum, and maximum for continuous variables and frequency and percentages for categorical variables.

Demographic data will include race, ethnicity, and age.

Baseline characteristics will include body weight, height, body mass index, and eGFR, HIV-1 infection, and enrollment distribution by randomization stratum (if applicable) will be summarized.

For the Randomized Cohort in Part 1, the Cochran–Mantel–Haenszel (CMH) test will be used to compare treatment arms for categorical demographic and baseline characteristics, and the Wilcoxon rank sum test will be used for continuous demographic and baseline characteristics. No comparison is needed for the Sentinel Cohorts in Part 1 and Part 2.

8.5. Efficacy Analysis

8.5.1. Primary Analysis

The primary efficacy endpoint is the proportion of subjects with HIV-1 RNA decreases from baseline exceeding $0.5 \log_{10}$ copies/mL at Day 15 for Part 1, Randomized Cohort. Subjects who have missing HIV-1 RNA values at Day 15 will be considered as without an HIV-1 RNA decrease from baseline exceeding $0.5 \log_{10}$ copies/mL at Day 15. The difference between each of the GS-9131 treatment groups and the placebo group will be compared using a Fisher's exact test at a two-sided significant level of 0.05.

The null hypothesis is that there is no difference in proportion of subjects with HIV-1 RNA decreases exceeding $0.5 \log_{10}$ at Day 15 between each of the GS-9131 treatment groups and the placebo group; the alternative hypothesis is that there is a difference in the proportion of subjects with HIV-1 RNA decreases exceeding $0.5 \log_{10}$ copies/mL at Day 15 between each of the GS-9131 treatment groups and the placebo group.

The primary analysis of the efficacy will be based on FAS in Part 1.

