- To evaluate the safety and efficacy of a regimen containing GS-9131 + bictegravir (BIC) + tenofovir alafenamide (TAF) through 24 weeks of treatment in subjects from Sentinel Cohort 2 and Randomized Cohort who switched from a failing regimen.

- To characterize the pharmacokinetics (PK) of GS-9131 in treatment-experienced patients.
- To evaluate the number of subjects with treatment-emergent nucleos(t)ide reverse transcriptase inhibitor (NRTI), protease inhibitor (PI), and integrase strand-transfer inhibitor (INSTI) mutations at the time of virologic failure.

Study Design:

Part 1: GS-9131 Functional Monotherapy

The study will consist of 3 cohorts - Two Sentinel Cohorts and one Randomized Cohort.

The Sentinel Cohort 1 will enroll 10 TE viremic HIV-1 subjects to receive open-label GS-9131 60 mg for 10 days in addition to their current failing ARV regimen.

Sentinel Cohort 2 will enroll up to 10 TE viremic HIV-1 subjects to receive open-label GS-9131 180 mg for 14 days in addition to their current failing ARV regimen.

Sentinel cohort subjects who meet criteria for Part 2, will transition to Part 2 and not participate in the randomized portion of this study.

The Sentinel Cohorts will be followed by a Randomized Cohort that is a double-blind comparison of the addition of GS-9131 (up to 180 mg), or PTM to the current failing ARV regimen in viremic HIV-1 positive adults. Randomization and dosing into the Randomized Cohort will begin after review of the clinical data in the second Sentinel Cohort.

In the Randomized Cohort, up to 48 subjects failing their current ARV regimen will be randomized 1:1:1:1 to GS-9131 (up to three active dose levels, up to 180 mg), or PTM. The GS-9131 dose for Treatment Arms A-C will be determined following review of the safety, activity and available PK data from Sentinel Cohort 2. GS-9131 will be added to their failing regimen for 14 days as follows:

Treatment Arms A-C: GS-9131 once daily + current failing antiretroviral therapy (ART) regimen (n=12 per Treatment Arm)

Treatment Arm D: PTM + current failing ART regimen (n=12)

Randomization will be stratified by HIV-1 RNA level ($\leq 100,000$ copies/mL and $> 100,000$ copies/mL) at screening.

Study medication will be administered by directly observed therapy (DOT).

**Part 2: GS-9131 + BIC + DRV + RTV or GS-9131 + BIC + TAF
Combination Therapy**

GS-9131(60 mg) + BIC (30 mg) + DRV(800 mg) + RTV(100 mg)
Regimen (Sentinel Cohort 1)

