8.5.2. Secondary Analyses

For Part 1 Randomized Cohort, the change from baseline in plasma \log_{10} HIV-1 RNA (copies/mL) and CD4 cell count at Day 15 will be summarized and compared between each of GS-9131 groups and placebo group using a two-sided Wilcoxon rank sum test at a two-sided significant level of 0.05.

For Part 1 Sentinel Cohorts, the proportion of subjects with HIV-1 RNA decreases from baseline exceeding $0.5 \log_{10}$ copies/mL at Days 11 (Sentinel Cohort 1) and 15 (Sentinel Cohort 2) and the change from baseline in plasma \log_{10} HIV-1 RNA (copies/mL) and CD4 cell count at Days 11 (Sentinel Cohort 1) and 15 (Sentinel Cohort 2) will be summarized using the Sentinel Cohort analysis set.

For Part 2, the percentage of subjects with plasma HIV-1 RNA < 50 copies/mL at Week 24, as defined by the FDA snapshot algorithm and missing = failure/excluded methods, will be summarized and the 95% confidence intervals using the Clopper-Pearson Exact method will also be presented. The change from Part 2 baseline in log₁₀ HIV-1 RNA, CD4 cell count and percentage at Week 24 will be summarized using descriptive statistics. These analyses will be based on the FAS in Part 2. As a sensitivity analysis these analyses will be repeated by utilizing subjects from randomized cohort only.

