8.9. Sample Size

For the Randomized Cohort in Part 1, a total of 48 HIV-1 positive adults, randomized in a 1:1:1:1 ratio to 4 arms (3 dose levels of GS-9131 up to 180 mg, and placebo) achieves 85% power to detect a 61.7% difference in the proportion of subjects with HIV-1 RNA decreases from baseline exceeding $0.5 \log_{10}$ between at least one of the GS-9131 treatment arms and placebo arm at Day 21. For sample size and power computation, it is assumed that 70% of subjects in each GS-9131 arm achieved a reduction exceeding $0.5 \log_{10}$ HIV-1 RNA while 8.3% of subjects in the placebo arm achieved such a reduction (based on internal Viread Study 907), and a Fisher's exact test at a two-sided significance level of 0.05 was conducted.

Sample size and power calculations were made using nQuery Advisor 6.0.

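### Randomization is stratified by screening HIV-1 RNA, but the planned efficacy tests use neither the stratum nor a baseline covariate: valid, with a modest and assumption-dependent loss of efficiency

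*Protocol*

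**What the plan says.** The Protocol Synopsis (Study Design) and Protocol 3.3 both state: "Randomization will be stratified by HIV-1 RNA level", with the cut at 100,000 copies/mL on the screening value.

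Protocol 8.5.1 defines the primary endpoint: "The primary efficacy endpoint is the proportion of subjects with HIV-1 RNA decreases from baseline exceeding" 0.5 log10 at Day 15. On the test it says "The difference between each of the GS-9131 treatment groups and the placebo group will be compared using a" plain Fisher test, two-sided at 0.05. Protocol 8.5.2 compares the Day 15 changes in log10 HIV-1 RNA and CD4 count between each active arm and placebo "using a two-sided Wilcoxon rank sum test at a two-sided significant level of 0.05".

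Neither section names the stratum, a covariate, or a stratified or adjusted sensitivity analysis. For the randomized comparison, 8.5.2 gives a test but no estimated difference or interval, although it does ask for 95% intervals on the Part 2 proportions. The Cochran-Mantel-Haenszel test appears only in 8.4, for comparing baseline characteristics. SAP 3.3 plans no stratified analysis. SAP 2.4 and 6 explain that the study stopped early and that the randomized cohort supplied no efficacy data.

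**The concern.** A variable judged important enough to constrain the randomization is then left out of every efficacy comparison, and no reason is given. Baseline HIV-1 RNA is measured in every subject, so using it costs no data. With 12 subjects per arm, recoverable precision matters.

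Two things are at stake. One is power, if the stratum or the baseline value predicts response. The other does not depend on any power assumption: in a study meant to choose a dose, the size of the viral-load difference at each dose, with its uncertainty, is a central result, and 8.5.2 does not specify it for the randomized comparison.

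**Working it through.** **1. Reproduce the plan's figure.** Inputs from Protocol 8.9: "it is assumed that 70% of subjects in each GS-9131 arm achieved a reduction exceeding" 0.5 log10, and "8.3% of subjects in the placebo arm achieved such a reduction"; the Synopsis gives 12 per arm. Power is the sum of Bin(a; 12, 0.70) × Bin(b; 12, 0.083) over all tables (a, b) with two-sided Fisher p ≤ 0.05. This gives **85.9%**, against 85% stated. It is the power of one pairwise unstratified comparison. The true size of that test at 12 v 12 is at most 2.3% over all common response rates, and 1.7% at a common rate of 30%.

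**2. Primary: exact stratified test v Fisher.** The statistic is T, the total number of responders on active. Given the margins in each stratum, the responders on active in that stratum are hypergeometric. The null distribution of T is the convolution over the two strata, and p is the sum of all probabilities no larger than that of the observed T. Power is by enumeration. Stratum shares and effects are assumed.

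*Equal stratum counts in both arms:*
- Same rates in both strata (70% v 8.3%), 1 to 6 of 12 per arm in the high stratum: 86.0–86.2% v 85.9%, a gain of 0.1–0.3 points.
- Overall rates held at 70% and 8.3%, with an assumed odds ratio for response between strata: gain 0.5–0.9 points at 3, 1.4–3.2 at 10, and 2.7–5.6 at an extreme 30.
- Assumed rates of 80%/10% (active/placebo) in the low stratum and 40%/3% in the high stratum. The between-stratum odds ratios are (0.80/0.20)/(0.40/0.60) = 6 on active and (0.10/0.90)/(0.03/0.97) = 3.6 on placebo:

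| High stratum, of 12 per arm | Stratified | Fisher | Gain (from unrounded values) |
|---|---|---|---|
| 2 | 90.2% | 90.1% | 0.0 |
| 3 | 88.7% | 87.1% | 1.6 |
| 4 | 85.4% | 83.5% | 2.0 |
| 6 | 78.0% | 74.9% | 3.1 |

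*Counts differing by one subject between arms:*
- Same rates, extra high-stratum subject on placebo: 87.4–88.8% v 85.9%, a gain of 1.5–2.9 points. With the extra subject on active the same enumeration gives slightly more, up to 3.5.
- Differing rates as above, counts off by at most one: gains of about 1–6 points. They are largest when the active arm holds the extra subject from the poorly responding stratum.
- Size at a 30% null: 2.8–2.9%, against 1.8–1.9% with balanced strata. Both are well under 5%.

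Much of the gain under imbalance arises because unequal counts break up the discreteness of the exact test. It is not all prognostic information recovered.

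The asymptotic CMH test is a false comparison. Without continuity correction it shows 93.0–94.0% at equal rates, but the unstratified chi-square already gives 93.9%, with a size of up to 6.4%. That difference comes from dropping Fisher's conservatism.

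**3. Secondary: ANCOVA on baseline v Wilcoxon, simulated, 12 per arm.** Under normality the planning rates imply an effect of z(0.70) − z(0.083) = 0.524 + 1.385 = 1.91 SD. At that effect Wilcoxon has about 99% and ANCOVA 99–100%.

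At an assumed 1-SD effect (difference 0.4, SD 0.4 log10):

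| Baseline–change correlation | Wilcoxon | ANCOVA | Gain |
|---|---|---|---|
| 0 | 61% | 62–64% | about level |
| 0.3 | 59–61% | 65–67% | about 4–6 |
| 0.5 | 60–61% | 73–76% | about 12–15 |

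At half the design effect (about 0.95 SD) Wilcoxon has 56–57%, and ANCOVA has 58–59%, 60–61%, 66% and 78% at correlations of 0, 0.2, 0.4 and 0.6.

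Stratifying the rank test alone (van Elteren, half the design effect, SD 0.5 assumed) is 3–4 points worse than Wilcoxon if the stratum has no effect, 1–2 worse at a 0.25 log10 stratum shift, and 3–7 better at 0.5.

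**The case against.** The case for leaving the plan alone is substantial. Fisher's test after stratified randomization is valid and conservative. The trial was sized for exactly this test, and it keeps the power claimed. Wilcoxon is a defensible choice at 12 per arm because it needs neither normality nor linearity. The documents give no stratum shares, no response rates by stratum and no baseline–change correlation, so every gain rests on assumptions. All of that stands, and it rules out calling the plan wrong.

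Three stronger readings are tempting and not supported:
- *That the plan ignores baseline.* Both endpoints are changes from the subject's own baseline, and 8.4 summarizes enrollment by stratum. The fair statement is that baseline is not modelled as a covariate. That still matters, because a change score can remain correlated with baseline.
- *That stratifying the primary test would reliably buy several points of power.* With strata balanced between arms, as stratified allocation intends, the gain is about 0–3 points. Larger figures need unequal stratum counts or a very strong stratum effect.
- *That the secondary test is underpowered as designed.* At the design effect both methods are near 99%. The gain appears only if the drug works less well than assumed. That is conceivable: Protocol 1.2.3.3 reports 2 of 11 subjects above 0.5 log at 60 mg, though over 10 days and at a lower dose than the 180 mg maximum planned for the randomized arms.

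The objection does not answer the missing effect estimate. Nor does it show a cost in power: the exact stratified test was never below Fisher in the settings checked, and ANCOVA showed no material loss at zero correlation.

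**Conclusion.** The mismatch is real: randomization is stratified, while the efficacy tests use no stratum or covariate and no between-arm estimate with a CI is planned for the change in log10 HIV-1 RNA. It costs efficiency, not validity, and the 85% is sound.

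For the primary test the loss is about 0–3 points with balanced strata and typically about 1–3 with counts off by one, more in some assumed settings. For the secondary test it is negligible at the design effect; at an assumed 1-SD effect it is about 4–6 points at correlation 0.3, 12–15 at 0.5, and nothing material at 0. The ANCOVA figures adjust for baseline only; adding the stratum uses one further degree of freedom.

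A reader might infer that reported results are affected. They are not, because the SAP has no randomized-cohort efficacy data to analyse. The point concerns the protocol's plan for that comparison and any reuse of it.

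**What to change.** - **Protocol 8.5.2:** analyse the Day 15 change in log10 HIV-1 RNA by ANCOVA on arm, baseline log10 HIV-1 RNA and screening stratum. Report the adjusted difference with 95% CI for each dose v placebo. Keep the unstratified Wilcoxon test as sensitivity analysis; a rank test that is only stratified can lose power.
- **Protocol 8.5.1:** use the exact stratified (conditional Mantel-Haenszel) test by screening HIV-1 RNA stratum for each dose v placebo, with Fisher as sensitivity analysis. State that an empty stratum contributes nothing, in which case the test reduces to Fisher. Do not substitute the asymptotic CMH test.

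Cost: minor rewording, including the power statements in the Synopsis, Protocol 8.9 and SAP 1.3, which now name Fisher's test, and a little programming. No new data are needed.
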